# Amendment B (03 Jun 2020):

This amendment was considered to be substantial based on the criteria set forth in Article 10(a) of Directive 2001/20/EC of the European Parliament and the Council of the European Union.

#### **Overall Rationale for the Amendment:**

The main purpose of this protocol amendment was to address regulatory comments regarding the primary endpoint.

Sections # and Name	Description of Change	Brief Rationale

 
1.1 Synopsis
 
3.0 Objectives and Endpoints
 
4.1 Overall Design
 
4.2 Scientific Rationale
 
8.1.1 COVID-19 Clinical Status
 
Assessment (Primary Endpoint
 
Assessments)
 
9.1 Statistical Hypotheses
 
9.2 Sample Size Determination
 
9.4.2 Primary Endpoint
 
	Updated primary endpoint	Response to FDA feedback. The updated primary endpoint is proportion of patients who die or require non- invasive ventilation/high-flow oxygen or invasive mechanical ventilation (including extracorporeal membrane oxygenation [ECMO]) by Day 28.
1.3 Schedule of Activities	Added clarification for Vital Signs to be assessed and documented daily.	Response to FDA feedback. Added clarifying test that Vital Signs are assessed and documented daily while hospitalized in the comment box in first position.

4.1 Overall Design

6.5.2 Required and Permitted

Concomitant Therapy

11.0 References

	Added statement allowing use of hydroxychloroquine and chloroquine only if recommended or required by local COVID-19 treatment guidelines.	Updated given updates in scientific literature.
5.1 Inclusion Criteria	Update to Criterion #3 to provide duration of time between confirmatory testing and enrollment	Response to FDA feedback. The updated criteria provide the duration of time between confirmatory testing and enrollment should not be more than 14 days for SARS-CoV-2 confirmation >72 hours.
5.2 Exclusion Criteria	Update to Criterion #11 with addition of clarifying text for patients that may have ongoing infection	Response to FDA feedback. The updated criterion includes "Note: Immunocompromised patients, patients with a chronic medical condition, or those taking a medication that cannot be discontinued at enrollment, who, in the judgment of the investigator, are at increased risk for serious infections or other safety concerns given the study products should be excluded".

Sections # and Name	Description of Change	Brief Rationale
5.2 Exclusion Criteria	Update to Criterion #22 that patients should not be enrolled in any other trials for COVID-19.	Response to FDA feedback. The updated criterion provides the participant should not be enrolled (start) in another clinical trial for the treatment of COVID-19 or SARS CoV-2 through Day 28.

5.2 Exclusion Criteria

6.5.3 Prohibited concomitant therapy

	Addition of Exclusion Criterion #25 for the use of extracorporeal blood purification (EBP) device to remove pro-inflammatory cytokines from the blood. Added EBP device to remove pro-inflammatory cytokines from the blood to list of prohibited concomitant therapy.	The new criterion was added and the prohibited concomitant therapy list updated given recent input on current practices and EUA that is in place and use of this modality can confound assessments in KHAA. The new exclusion criterion applies if "Are using or will use extracorporeal blood purification (EBP) device to remove pro-inflammatory cytokines from the blood such as a cytokine absorption or filtering device, for example, CytoSorb ®."
5.2 Exclusion Criteria	Addition of Exclusion Criterion #26 to exclude patients that are unlikely to survive participation in the study	The new criterion provides exclusion if the patient, in the opinion of the investigator, unlikely to survive for at least 48 hours after screening.
9.3 Populations for Analyses	Addition of clarification of analyses population	The new language provides that a sensitivity analysis excluding patients who die within 24 hours of randomization and have do not resuscitate (DNR) or do not intubate (DNI) in ITT/PP analyses populations will be conducted.

# Amendment A (27 May 2020):

Amendment A occurred before any study participant was consented or dosed at any study site.

#### **Overall Rationale for Amendment A:**

The main purpose of this protocol amendment was to address regulatory comments regarding the primary endpoint and regarding the role of an internal assessment committee in the review of unblinded data.

anged primary endpoint. anged wording of primary jective.	Response to FDA feedback. The new primary endpoint is proportion of patients requiring non-invasive ventilation/high-flow oxygen or invasive mechanical ventilation (including extracorporeal membrane oxygenation [ECMO]) by Day 28. A related secondary endpoint ["Proportion of patients requiring mechanical ventilation (Day 1 to Day 28)"] has been removed; this secondary objective is unnecessary given the new primary endpoint. The primary objective wording was changed (from "on clinical
	proportion of patients requiring non-invasive ventilation/high-flow oxygen or invasive mechanical ventilation (including extracorporeal membrane oxygenation [ECMO]) by Day 28. A related secondary endpoint ["Proportion of patients requiring mechanical ventilation (Day 1 to Day 28)"] has been removed; this secondary objective is unnecessary given the new primary endpoint. The primary objective wording was
ective.	non-invasive ventilation/high-flow oxygen or invasive mechanical ventilation (including extracorporeal membrane oxygenation [ECMO]) by Day 28. A related secondary endpoint ["Proportion of patients requiring mechanical ventilation (Day 1 to Day 28)"] has been removed; this secondary objective is unnecessary given the new primary endpoint. The primary objective wording was
	oxygen or invasive mechanical ventilation (including extracorporeal membrane oxygenation [ECMO]) by Day 28. A related secondary endpoint ["Proportion of patients requiring mechanical ventilation (Day 1 to Day 28)"] has been removed; this secondary objective is unnecessary given the new primary endpoint. The primary objective wording was
	ventilation (including extracorporeal membrane oxygenation [ECMO]) by Day 28. A related secondary endpoint ["Proportion of patients requiring mechanical ventilation (Day 1 to Day 28)"] has been removed; this secondary objective is unnecessary given the new primary endpoint. The primary objective wording was
	membrane oxygenation [ECMO]) by Day 28. A related secondary endpoint ["Proportion of patients requiring mechanical ventilation (Day 1 to Day 28)"] has been removed; this secondary objective is unnecessary given the new primary endpoint. The primary objective wording was
	membrane oxygenation [ECMO]) by Day 28. A related secondary endpoint ["Proportion of patients requiring mechanical ventilation (Day 1 to Day 28)"] has been removed; this secondary objective is unnecessary given the new primary endpoint. The primary objective wording was
	Day 28. A related secondary endpoint ["Proportion of patients requiring mechanical ventilation (Day 1 to Day 28)"] has been removed; this secondary objective is unnecessary given the new primary endpoint. The primary objective wording was
	A related secondary endpoint ["Proportion of patients requiring mechanical ventilation (Day 1 to Day 28)"] has been removed; this secondary objective is unnecessary given the new primary endpoint. The primary objective wording was
	["Proportion of patients requiring mechanical ventilation (Day 1 to Day 28)"] has been removed; this secondary objective is unnecessary given the new primary endpoint. The primary objective wording was
	mechanical ventilation (Day 1 to Day 28)"] has been removed; this secondary objective is unnecessary given the new primary endpoint. The primary objective wording was
	28)"] has been removed; this secondary objective is unnecessary given the new primary endpoint. The primary objective wording was
	secondary objective is unnecessary given the new primary endpoint. The primary objective wording was
	given the new primary endpoint. The primary objective wording was
	The primary objective wording was
	improvement of patients" to "on
	disease progression in patients") to
	align with the primary endpoint.
ded a secondary endpoint	Response to FDA feedback.
aca a secondary enapoint.	The new secondary endpoint is overall
	improvement in NIAID ordinal scale
	evaluated at Day 10. It has been
	incorporated into the existing key
	secondary endpoint of "Overall
	improvement on the NIAID-OS
	evaluated at Day 4, Day 7, Day 10,
	Day 14."
moved timenoint indicator for	Changed to maintain consistency with
	changed primary endpoint described
primary enapoint.	above.
nlaced "creatinine kinase"	Changed to fix typographical error.
-	changed to fix typographical criot.
	Changed to prevent misreading.
	changed to prevent misreading.
	New information is included for
	consistency with the new primary
mary enupoint.	endpoint.
	ded a secondary endpoint. noved timepoint indicator for primary endpoint. blaced "creatinine kinase" n "creatine kinase." noved a statement about use bygen therapy at time of ty entry. vided rationale for the new nary endpoint.

Sections # and Name	Description of Change	Brief Rationale
8.1.1 COVID-19 Clinical Status	Added two paragraphs defining	Changed for consistency with other
Assessment	terms relevant to the primary endpoint.	listed changes and to improve clarity.
8.1.3 Other Efficacy Assessment	Added "high-flow oxygen" to the endpoint cell for non- invasive ventilation.	Changed for consistency with other listed changes and to improve clarity.
8.2.4 Chest Imaging Studies	Added "or appropriate physician" to the list of personnel who may assess the chest imaging scans.	Changed to provide flexibility to sites.
8.2.5 Laboratory Tests 10.2.1 Clinical Laboratory Tests	Changed the requirements for documentation of reviews of laboratory reports.	Changed to decrease site burden, allowing flexibility on how the review is documented.
9.2 Sample Size Determination	Modified rationale for sample size.	Changed to align with response to FDA feedback, and to use more recently available data as part of the justification of sample size.
9.4.1 General Considerations	Added Wilcoxon rank sum test for treatment comparison of ventilation-free days.	Changed for consistency with changes in other sections.
9.4.2 Primary Endpoint	Revised primary endpoint. Added statement about how patients on non-invasive ventilation at baseline will be counted in the new endpoint.	Changed as a result of response to FDA feedback.
9.4.3 Secondary Endpoints	Removed secondary endpoints, as previously described.	See above.

9.5 Interim Analyses

9.6 Data Monitoring Committee

10.1.5 Committee Structure

10.1.9 Study and Site Start and Closure

	Removed all references to Internal Assessment Committee (IAC). Clarified the use of interim analyses.	Response to FDA feedback. Unblinded data reviews will be carried out by the external Data Monitoring Committee (DMC), not an IAC.
10.5 Appendix 5: Abbreviations	Added and removed abbreviations.	Editorial. Changed for consistency with other changed sections.
11 References	Added and removed references.	Editorial. Changed for consistency with other changed sections.

### 3. Revision History

Statistical analysis plan (SAP) Version 1 was approved prior to first unblinding.

Statistical analysis plan Version 2 was approved prior to Data Monitoring Committee 3 (DMC3).

Statistical analysis plan Version 3 was approved prior to Data Monitoring Committee Meeting 6.

Statistical analysis plan Version 4 was approved prior to unblinding of the study team for the primary outcome database lock.

The main changes incorporated in SAP Version 4 are as follows:

Change	Section	Summary of Changes
Minor changes to increase clarity and correct spelling and grammatical errors	Throughout	To increase accuracy and clarity.
General Considerations	Table KHAA.6.1	Indicated that p-values for primary and key secondary analyses will be reported to as many decimal places as needed.
Analysis Populations	6.1.1	Removed the As Treated Population, as it very similar to the Safety Population.
Definition of Study Baseline	6.1.2	Changed the definition of baseline for efficacy and health outcomes to be relative to the first date that clinical status is assessed rather than first study drug dose. This is consistent with basing these analyses on the ITT population.
Definition of Study Period Time Intervals	Table KHAA.6.2	Removed 2 periods from the Definition of Study Period Time Intervals. Instead, these will be described in analyses, as needed.
Baseline Stratification Variables	6.1.4	Added a section on baseline stratification variables so that these can be referred to throughout the document.
Logistic Regression Model	6.2.1	Changed text regarding logistic regression model, mainly to accommodate multiple imputation.
Analysis of Variance/Covariance	6.2.2	Clarified models for ANOVA
Time-to-Event Analysis	6.2.3	Clarified models for time-to-event analyses.
Proportional Odds Model	6.2.4	Clarified the model for proportional odds analyses

Change	Section	Summary of Changes
Last Observation Carried Forward (LOCF)	6.4.2	Changed mLOCF to LOCF, as it more closely matches the planned analyses. There aren't separate rules in for different intercurrent events.
Multiple Imputation	6.4.3	Filled in details of planned multiple imputation analyses.
Multiple Comparisons/Multiplicity	6.6	Corrected language regarding the multiplicity testing.
Description and Derivation of Primary, Key Secondary, and Associated Supportive Analyses	Table KHAA.6.4	Added derivation details for several variables
Description of Primary, Key Secondary, and Associated Supportive Analysis	Table KHAA.6.5	Minor wording changes for clarity. Changed mLOCF to LOCF. Changed analysis for Oxygen Saturation from MI to LOCF.
Description and Derivation of Other Secondary Outcomes	Table KHAA.6.6	Added analytic details for several analyses.
Description of Other Secondary Analyses	Table KHAA.6.7	Removed analysis of time to recovery by disease duration at baseline.  Removed Fine-Gray proportional hazards regression with death as a competing risk, as death is already handled in a manner that considers it a competing risk (i.e., via IETI).
Primary Outcome and Methodology	6.11.1	Changed the final allocation of alpha for Population 1 to 99%. This change was made based on a review of blinded data that showed that Population 2 had a much smaller sample size than originally anticipated.
Key Secondary Efficacy Analyses	6.11.2	Added an analysis of all-cause mortality in the safety population.
Subgroup Analyses	6.14	Updated subgroup analyses to reflect current plans.
Interim Analyses and Data Monitoring	6.16	Removed the paragraph that suggested that a limited number of preidentified individuals may gain access to the limited unblinded data, as there is no plan to do early unblinding for PK/PD analyses.
Sample Size Re-Estimation	6.16.2	Removed the clause "(in addition to the final analysis)" as the 90% allocation of $\alpha$ to Population 1 only applied to the

Change	Section	Summary of Changes
		sample size re-estimation. For the final primary outcome analyses, 99% will be allocated to Population 1.
References	8	Added new references
Multiple Imputation	Appendix 2	Added appendix with details of the multiple imputation methodology
Exploratory Analyses	Appendix 3	Added appendix with additional exploratory analyses

Abbreviations: ANOVA = analysis of variance; DMC = Data Monitoring Committee; DOH = duration of hospitalization; IETI = infinite event time imputation; VFD = ventilator-free days.

## 4. Study Objectives

### 4.1. Primary Objective

Objectives	Endpoints
Primary	
To evaluate the effect of baricitinib 4-mg once daily (QD) compared to placebo on disease progression in patients with COVID-19 infection	Proportion of patients who die or require non-invasive ventilation/high-flow oxygen or invasive mechanical ventilation (including extracorporeal membrane oxygenation [ECMO]) by Day 28 in the following populations: 
 
Population 1 - all randomized patients
 
Population 2 – patients who, at baseline, require oxygen supplementation (OS 5 and 6) and are not receiving dexamethasone or other systemic corticosteroids for the primary study condition.
 

The associated estimand for this objective is to measure the effect of treatment with baricitinib as assessed by proportion of patients who die or progress to requiring non-invasive ventilation/high-flow oxygen or invasive mechanical ventilation (including extracorporeal membrane oxygenation [ECMO]) by Day 28.

### 4.2. Secondary Objectives

Note that all secondary objectives apply to Population 1.

Objectives	Endpoints
Key Secondary	
To evaluate the effect of baricitinib 4-mg QD compared to placebo on clinical outcomes in patients with COVID-19 infection	Proportion of patients with at least 1-point improvement on NIAID-OS or live discharge from hospital at Day 4, Day 7, Day 10, Day 14
	Number of ventilator-free days (Day 1 to Day 28)
	Time to recovery (NIAID-OS) (Day 1 to Day 28)
	Overall improvement on the NIAID-OS evaluated at Day 4, Day 7, Day 10, Day 14
	Duration of hospitalization (Day 1 to Day 28)
	Proportion of patients with a change in oxygen saturation from <94% to ≥94% from baseline to Day 4, Day 7, Day 10, Day 14
	All-cause mortality (Day 1 through Day 28)
Other Secondary	
To evaluate the effect of baricitinib 4-mg QD compared to placebo on other clinical outcomes in patients with COVID-19 infection	Treatment Period – (Day 1 to Day 28, unless otherwise specified) 
 
Time to recovery (NIAID-OS) by disease duration of <7 days or ≥7 days
 
Duration of stay in the intensive care unit (ICU) in days
 
Time to clinical deterioration (one-category increase on the NIAID-OS)
 

Objectives	Endpoints
	
 
• Time to clinical improvement in one category of the NIAID-OS
 
• Time to resolution of fever, in patients with fever at baseline
 
• Overall improvement on the NIAID-OS evaluated at Day 21, Day 28
 
• Mean change in National Early Warning Score (NEWS)
 
• Time to definitive extubation
 
• Time to independence from non-invasive mechanical ventilation
 
• Time to independence from oxygen therapy in days
 
• Time to oxygen saturation of <math>\geq 94\%</math> on room air in days
 
• Number of days with supplemental oxygen use
 
• Number of days of resting respiratory rate <math>< 24</math> breaths per minute
 

Other Secondary	
	
Landmark analyses – Day 4, Day 7, Day 10, Day 14, Day 28
 
 
• Proportion of patients in each severity category on the NIAID-OS
 
• Proportion of patients with at least 2-point improvement on the NIAID-OS or live discharge from the hospital
 
• Proportion of patients with at least 1-point improvement on NIAID-OS or live discharge from hospital
 

Abbreviations: NIAID-OS = National Institute of Allergy and Infectious Diseases ordinal scale; QD = once daily.

### 4.3. Exploratory Objectives

Exploratory

Exploratory objectives and endpoints may include the following: Serum cytokines, hs-CRP, D-dimer, lactate dehydrogenase (LDH), ferritin (baseline, and during treatment up to Day 14)
 
 
• Virologic measures
 
• To characterize PK of baricitinib in intubated patients with COVID-19 infection
 
• Long-term (at least Day 60) clinical outcomes.
 

Abbreviations: hs-CRP = high-sensitivity C-reactive protein; PK = pharmacokinetics.

Planned analyses for long-term clinical outcomes and for patients participating in Addendum 5, who are OS 7 at baseline, are included in [Appendix 3](#).

[figure not shown]
## 5. Study Design

### 5.1. Summary of Study Design

Study I4V-MC-KHAA (KHAA) is Phase 3, multicenter, randomized, double-blind, placebo-controlled, parallel-group study designed to evaluate the efficacy and safety of baricitinib 4-mg given once daily (QD). The primary endpoint is the proportion of patients who die or require non-invasive ventilation/high-flow oxygen or invasive mechanical ventilation (including ECMO) by Day 28.

The study duration will be up to approximately 60 days over 3 study periods (see [Figure KHAA.5.1](#)):

- Screening: on Day 1 prior to dosing
- Treatment period: treatment is administered for up to 14 days, or up to the day of hospital discharge, whichever comes first, followed by treatment evaluations up to Day 28; and
- Follow-up: period starting after treatment evaluation, with a follow-up visit approximately 28 days after last dose of study drug and another follow-up visit at approximately Day 60.

Abbreviations: D = day; QD = once daily.

Note: Dosing occurs from the day of randomization until Day 14, or until hospital discharge, whichever comes first. Placebo or baricitinib are given with background therapy in keeping with local clinical practice for management of COVID-19, as defined in the protocol.

**Figure KHAA.5.1. Schema of Study I4V-MC-KHAA.**

Patients will be enrolled if they are hospitalized with coronavirus (SARS-CoV-2) infection and meet other study entry criteria. Patients requiring invasive mechanical ventilation (including ECMO) at the time of study entry are not eligible (unless they are enrolled in Addendum 5.0, which allows such patients).

While hospitalized, enrolled patients will receive either baricitinib or placebo until Day 14 or until the day of hospital discharge, whichever comes first.

A follow-up visit approximately 28 days after last dose is required for all randomized patients, including those discharged from the hospital before Day 14. Another follow-up visit occurs at approximately Day 60. The follow-up visits can be conducted as telephone visits.

Discharge from the hospital prior to Day 14 is not considered early discontinuation from the study drug or from the study. All randomized patients, including patients meeting criteria for early discontinuation of study drug, as specified in KHAA Protocol (Section 5.1) should be encouraged to remain in the study for the scheduled study assessments specified in the Schedule of Activities (SoA) (Protocol Section 1.3). Patients who prematurely discontinue from the study should have an early termination visit (ETV) and final follow up visit, if possible, as shown in the SoA.

## 5.2. Determination of Sample Size

In protocol amendment e, the final amendment, the sample size was updated to approximately 1400 patients based on blinded review of the proportion of patients requiring oxygen supplementation without the use of dexamethasone or systemic corticosteroids at baseline and the potential that concomitant use of systemic corticosteroids may reduce the magnitude of the treatment effect.

The table below describes the power calculations for various scenarios with a total sample size of 1400. This assumes, for illustration, that  $\alpha_1$  for Population 1 is 75% of the total alpha and that 60% of the patients were taking dexamethasone or other corticosteroids at baseline.

Treatment Effect Size in Patients Who are at OS 5 or OS 6 at Baseline		Combined Effect Size	Power for at Least One of the Two Primaries to Succeed
Patients using dexamethasone or a systemic corticosteroid	Patients not using dexamethasone or a systemic corticosteroid		
0.075	0.075	0.075	81%
0.040	0.075	0.054	54%

Abbreviations: NIAID = National Institute of allergy and Infectious Diseases; OS 5 = #5 on the 8-point NIAID ordinal scale - Hospitalized, requiring supplemental oxygen; OS 6 = #6 on the 8-point NIAID ordinal scale – Hospitalized, on noninvasive ventilation or high-flow oxygen devices.

Note: Power estimates were obtained from a custom simulation program.

Amendment e also allowed for the sample size to be increased using an unblinded sample size re-estimation (Gao et al. 2008) during an interim analysis (that occurred in January 2021).

## 5.3. Method of Assignment to Treatment

Blinding will be maintained in the Phase 3 study.

Method of treatment assignment

Patients who meet all criteria for enrollment will be randomized in a 1:1 ratio (baricitinib 4-mg: placebo) at Day 1.

Randomization will be stratified by these factors:

- disease severity by ordinal scale (OS):
  - hospitalized not requiring supplemental oxygen, requiring ongoing medical care (OS 4)
  - hospitalized requiring supplemental oxygen by prongs or mask (OS 5)
  - hospitalized requiring non-invasive ventilation or high-flow oxygen (OS 6)
- age (<65 years; ≥65 years)
- region (US, Europe, rest of world), and
- dexamethasone and/or other systemic corticosteroid used at baseline for primary study condition (Yes/No). (Note that the original protocol included symptom onset <7 days or ≥7 days prior to randomization as a stratification factor. It was changed to this one in Amendment (c).)

Assignment to treatment groups will be determined by a computer-generated random sequence using an interactive web-response system (IWRS).

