# **Protocol Amendment Summary of Changes Table**

DOCUMENT HISTORY									
Document	Date								
Original Protocol	18 May 2020								
Amendment A	27 May 2020								
Amendment B	03 Jun 2020								
Amendment C	12 Aug 2020								
Amendment D	20 Oct 2020								

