	citations; updated year of United	citations added; UPSI was updated.
	States package insert (USPI)	
4.3 Justification for Dose	Replaced "data on file" with citation	Information has been published,
		citation added.

Sections # and Name	Description of Change	Brief Rationale
5.2 Exclusion Criteria	Added a note to exclusion criterion #8	To clarify corticosteroid use (dose and duration) for dexamethasone and/or other systemic corticosteroids
5.2 Exclusion Criteria	Added "or" in the phrase about deep vein thrombosis and pulmonary embolism	To clarify and support site understanding
5.2 Exclusion Criteria	Added a parenthetical reference to the aforementioned exclusion criteria following exclusion criterion #20	To support site understanding
6.1 Study Interventions Administered	Clarified dosing instructions for patients with eGFR >30 mL/min/1.73 m  to <60 mL/min/1.73 m  at screening	To support site understanding
6.3 Measures to Minimize Bias: Randomization and Blinding	Changed one of the factors for stratification: removed the symptom onset factor, and added a factor about use of dexamethasone and/or other systemic corticosteroid use at baseline for primary study condition	To accommodate evolving changes in standard-of-care therapy
6.6 Dose Modification	Clarified dosing instructions for patients with eGFR >30 mL/min/1.73 m  to <60 mL/min/1.73 m  at screening	To support site understanding
8.1.3 Other Efficacy Assessments	Clarified text on resolution of fever	To clarify the definitions and options for assessment of fever
8.2.1 Vital Signs	Revised text about body temperature, simplifying the text	To avoid redundancy and potential inconsistency. Section 8.1.3 provides the information about body temperature.
8.2.3 Electrocardiograms	Revised text about timing of ECGs that are acceptable, per the SOA	To keep text consistent with changes in the SOA, as described above
8.2.4 Chest Imaging Studies	Revised text about timing of imaging that is acceptable, per the SOA	To keep text consistent with changes in the SOA, as described above
8.8 Biomarkers	Added text about sample collection based on availability of centrally supplied lab kits	To clarify collection based on lab kit availability
9.2 Sample Size Determination	Changed the number of patients to be randomized, changed power; changed assumptions for the power calculation	To accommodate evolving changes in standard-of-care therapy

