### 6.1.4. Baseline Stratification Variables

Throughout the SAP, when baseline stratification variables are referred to, they include the following categorical variables:

- baseline disease severity (ordinal scale [OS] 4, OS 5, OS 6),
- age (<65 years, ≥65 years),
- region (US, Europe, rest of world) and
- dexamethasone and/or other systemic corticosteroid used at baseline for primary study condition (Yes/No).

If any of these are redundant for a particular model they will be dropped.

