### **6.2.1. Logistic Regression Model**

Treatment comparisons of discrete/binary efficacy variables between treatment groups will be made using a logistic regression analysis adjusted for baseline stratification variables (Section 6.1.4). The p-value and odds ratio with 100(1- $\alpha$ )% confidence interval (CI) from the logistic model will be reported.

Point estimates for proportions and difference in proportions will be presented. Confidence intervals and p-values for the estimates of the differences of the proportions and will be presented. For last-observation-carried-forward (LOCF) analyses the CIs will be based on the Newcombe-Wilson method without continuity correction. For multiple imputation analyses, percentages will be based on the observed percentages; CIs will be based on the Wald method without continuity correction.

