## 6.14. Subgroup Analyses

For primary and gated secondary endpoints, following subgroup analysis will be conducted:

- baseline disease severity:
  - hospitalized not requiring supplemental oxygen, requiring ongoing medical care (OS 4)
  - hospitalized requiring supplemental oxygen by prongs or mask (OS 5)
  - hospitalized requiring noninvasive ventilation or high-flow oxygen (OS 6)
  - OS 5 and OS 6 combined
- baseline steroid use: dexamethasone and/or other systemic corticosteroid used at baseline for primary study condition (Yes/No)
- baseline remdesivir use (Yes/No)

The following subgroups categorized into disease-related characteristics and demographic characteristics will be evaluated for primary endpoint. These analyses may also be conducted selectively on key secondary endpoints if applicable:

- patient demographic and characteristics subgroups:
  - gender (male, female)
  - age group (<65, ≥65)
  - baseline weight (<60 kg, ≥60 to <100 kg, ≥100 kg)
  - baseline BMI (<25 kg/m^2, ≥25 to <30 kg/m^2, ≥30 kg/m^2)
  - race (American Indian or Alaska Native, Asian, Black or African American, Native Hawaiian or Other Pacific Islander, White, Multiple)
  - baseline renal function status: impaired (eGFR <60 mL/min/1.73 m^2) or not impaired (eGFR ≥60 mL/min/1.73 m^2)
- geographic region subgroups:
  - region (US, Europe, Rest of World)
- baseline disease-related characteristics subgroups:
  - baseline disease duration of symptoms prior to enrollment:<7 days, ≥7 days

- preexisting comorbid conditions of interest: none, any

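### Symptom onset (<7 / ≥7 days) was a randomisation stratum until Amendment C but is missing from the covariates of the primary and key secondary regression models

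*SAP*

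**What the plan says.** SAP Section 5.3, after listing the current factors, adds: "Note that the original protocol included symptom onset" (<7 or ≥7 days before randomisation) as a stratification factor, and says that Amendment C changed it to the corticosteroid factor. The protocol's amendment history (Appendix 10.6, Amendment C, Section 6.3 entry) agrees: the change "removed the symptom onset factor, and added a factor about use of dexamethasone" or other systemic corticosteroids at baseline. The document history dates Amendment C to 12 August 2020. Neither document says how many patients were randomised under the old scheme.

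SAP Section 6.1.4 fixes the covariate list for the whole plan: "Throughout the SAP, when baseline stratification variables are referred to, they include the following categorical variables". Four follow: baseline ordinal-scale severity, age group, region and baseline corticosteroid use. Sections 6.2.1 (logistic), 6.2.2 (ANOVA), 6.2.3 (Cox) and 6.2.4 (proportional odds) all refer to that list. No reason is given for leaving symptom onset out.

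The variable is otherwise in the plan. The onset of symptoms is recorded on Day 1 (protocol Section 1.3). The 7-day split is a baseline characteristic (SAP 6.8.2), an other secondary analysis of time to recovery (SAP 4.2) and a subgroup for the primary endpoint, listed in SAP 6.14 as "baseline disease duration of symptoms prior to enrollment". In that subgroup analysis it enters a model, as the subgroup term with its treatment interaction.

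**The concern.** Protocol Sections 9.4.1 and 9.4.2 and SAP 6.11.1 promise models that include the baseline stratification factors. For patients randomised before Amendment C took effect, symptom onset was one of them, yet the models ignore it. When randomisation is balanced on a prognostic factor and the model omits it, the test tends to be conservative for those patients. Baseline information that is already being collected also goes unused in every adjusted analysis.

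That the factor applied to only part of the trial does not explain the omission. Corticosteroid use was a stratum only from Amendment C onward, yet Section 6.1.4 adjusts all patients for it. At stake is a small amount of power for the primary endpoint and the adjusted key secondaries. The key secondaries are tested in sequence, so a failure early in the order blocks the later ones.

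**Working it through.** **1. The plan's own power figure.** The latest power statement with all inputs given is Amendment D in protocol Section 9.2: N = 1000, placebo 25%, two-sided alpha 0.05, stated power 47% for a 5-point and 83% for a 7.5-point difference. A two-proportion calculation with 500 per arm gives 47.3% and 82.7%, so it reproduces. The Amendment E table (81% and 54%) gives no placebo rate. A bivariate-normal version gives 91.6% and 69.4% at 25%, and 80.8% and 56.1% at an assumed 40%. Those figures can be neither confirmed nor called wrong, and this point does not rest on them.

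**2. Inputs for the check.** From the documents: N = 1400 (700 per arm), 1:1 allocation, one-sided alpha 0.025, placebo rate 25% (Amendment D), and differences of 5.4 and 7.5 points (the combined effects in the Amendment E table). Assumed, because the documents do not give them: an onset odds ratio of 1.5, 2 or 3; 20 to 40% of patients in the higher-risk onset category; 10 to 50% randomised before Amendment C. Population 1 only, without the alpha split and without the other covariates.

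**3. One worked case: 5.4 points (25% against 19.6%), onset OR 2, 30% in the higher-risk category.**

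Without onset:
- Log OR = ln(0.196/0.804) − ln(0.25/0.75) = −0.313.
- SE = √(1/175 + 1/525 + 1/137.2 + 1/562.8) = 0.1292.
- Power = Φ(0.3129/0.1292 − 1.960) = 67.8%.

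With onset, choose the intercept a in each arm so that 0.3·expit(a + ln 2) + 0.7·expit(a) equals that arm's overall rate:
- Placebo a = −1.331 and baricitinib a = −1.650, so the conditional log OR = −0.319.
- Cell weights n·p(1−p): lower-risk category 81.0 (placebo) and 66.2 (baricitinib); higher-risk category 47.5 and 42.1.
- Information = 81.0×66.2/147.2 + 47.5×42.1/89.6 = 58.75, so SE = 1/√58.75 = 0.1305.
- Power = Φ(0.3191/0.1305 − 1.960) = 68.7%.

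The gain is 0.85 points before rounding. The SE rises from 0.1292 to 0.1305; power improves because the conditional log odds ratio grows by proportionally more.

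**4. The same calculation over the assumed ranges: gain in power, percentage points.**

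| Onset OR | 5.4 points; 20 / 30 / 40% share | 7.5 points; 20 / 30 / 40% share |
|---|---|---|
| 1.5 | 0.22 / 0.28 / 0.30 | 0.11 / 0.14 / 0.16 |
| 2 | 0.69 / 0.85 / 0.90 | 0.36 / 0.43 / 0.46 |
| 3 | 1.89 / 2.22 / 2.26 | 0.95 / 1.10 / 1.12 |

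If the higher-risk category is the larger one, the gain is smaller: at OR 3 with 80% in that category and 5.4 points, it is 0.93.

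**5. Type I error and power by simulation.** 200,000 trials per scenario; patients before Amendment C balanced within onset category, later patients not; Wald test from the logistic model.
- One-sided type I error: 0.0232 to 0.0255 with onset omitted, 0.0240 to 0.0258 with it included. The Monte Carlo standard error is about 0.0004.
- Bounding case (every patient stratified on onset, OR 3): 0.0218 omitted, 0.0253 included.
- Power at 7.5 points: 93.0 to 93.3% omitted, 93.1 to 94.2% included. At 5.4 points: 68.0 to 68.4% omitted, 68.2 to 70.4% included.
- Gain within scenarios: about 0.1 to 2.2 points, in line with step 4.

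**The case against.** The omission is neither hidden nor a contradiction. SAP 5.3 discloses the change, and the list in 6.1.4 matches the current factors in protocol Section 6.3. Type I error is sound either way, so this is optional covariate adjustment. The benefit rests on an odds ratio, a category split and a share of early patients that the documents do not give. The check leaves out severity, age, region and corticosteroid use; if onset is correlated with any of them, the added gain is smaller. A one-line justification or a single sensitivity analysis of the primary endpoint might be thought enough. All of this stands as a limit on the size of the point. It does not supply a reason for treating onset differently from corticosteroid use.

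Four stronger readings are tempting, and the documents and the check support none of them.
- **That the primary test is invalid or anti-conservative.** The check shows no inflation.
- **That adjustment shrinks the standard error.** In the logistic model it rises slightly.
- **That onset is available for everyone, so the change is free.** SAP Table KHAA.6.6 foresees a missing disease duration, and SAP 6.1 excludes patients who lack a model covariate. A separate missing category is not a safe remedy: protocol 9.4.1 falls back to Fisher's exact test when any category of a factor has fewer than 5 responders. SAP 6.2.1 does not repeat that rule, but the protocol retains it. The risk is greatest in Population 2, which the SAP revision history describes as much smaller than expected.
- **That every key secondary would benefit.** Time to recovery and mortality are tested by the unstratified log-rank test; their Cox models are only supportive.

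**Conclusion.** The point holds as a small, low-priority improvement. A factor that governed randomisation of the early patients is left out of the primary and key secondary regression models without explanation, while a factor that governed only the later patients is included for all. Omission costs no validity; at most it makes the test slightly conservative. The expected gain from inclusion is about 0.1 to 0.3 points of power at an onset odds ratio of 1.5, 0.4 to 0.9 at 2 and 1 to 2.3 at 3. These figures assume N = 1400, a 25% placebo rate, true differences of 5.4 to 7.5 points and 20 to 40% of patients in the higher-risk category. They concern the logistic primary analysis in Population 1; the gain in the ANOVA and proportional odds models was not sized.

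**What to change.** In SAP Section 6.1.4, add symptom onset before randomisation (<7 days, ≥7 days) to the baseline stratification variables, derived from the case report form for all patients. A randomisation-system value is presumably held only for those randomised before Amendment C. State in advance that a patient with a missing onset date is assigned to the more frequent category. Such patients are then neither dropped under the covariate rule in SAP 6.1 nor placed in a sparse category that could trigger the protocol 9.4.1 fallback. Where onset is itself the subgroup, the existing redundancy rule in 6.1.4 removes the duplicate term.

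The cost is one degree of freedom per model and one simple rule for missing onset. Section 6.1.4 was itself introduced in SAP Version 4, approved before the study team was unblinded for the primary outcome lock, so the covariate list was being settled at that stage. The log-rank and Wilcoxon analyses need no change.
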